1.0 Background

- 1.1 Melanoma is the fifth most common cancer in men and sixth most common in women in the United States with an estimated ten thousand deaths a year. Recent advances in systemic therapy for metastatic melanoma have dramatically improved outcomes; however, the majority of patients ultimately die from their disease.
- 1.2 One of the major breakthroughs for the treatment of metastatic melanoma is the immunotherapy pembrolizumab (MK-3475). Pembrolizumab has demonstrated dramatic clinical activity in patients with metastatic melanoma inducing response rates in ~20-40% of patients. In addition, the majority of these responses are durable which will likely result in significant improvement in long-term survival for patients. Despite the success of pembrolizumab in a large minority of patients, the majority of patients ultimately go on to progress and require additional therapy.
- 1.3 Approximately 20-30% of patients with metastatic melanoma have metastatic cutaneous lesions that are amenable to treatment with the combination of systemic therapy with topical or injectable therapy.
- 1.4 Pharmaceutical and Therapeutic Background on Pembrolizumab
 - 1.41 The importance of intact immune surveillance in controlling outgrowth of neoplastic transformation has been known for decades. Accumulating evidence shows a correlation between tumor-infiltrating lymphocytes (TILs) in cancer tissue and favorable prognosis in various malignancies. In particular, the presence of CD8⁺ T-cells and the ratio of CD8⁺ effector T-cells / FoxP3⁺ regulatory T-cells seems to correlate with improved prognosis and long-term survival in many solid tumors.
 - 1.42 The PD-1 receptor-ligand interaction is a major pathway hijacked by tumors to suppress immune control. The normal function of PD-1, expressed on the cell surface of activated T-cells under healthy conditions, is to down-modulate unwanted or excessive immune responses, including autoimmune reactions. PD-1 (encoded by the gene *Pdcd1*) is an Ig superfamily member related to CD28 and CTLA-4 which has been shown to negatively regulate antigen receptor signaling upon engagement of its ligands (PD-L1 and/or PD L2). The structure of murine PD-1 has been resolved. PD-1 and family members are type I transmembrane glycoproteins containing an Ig Variable-type (V-type) domain responsible for ligand binding and a cytoplasmic tail which is responsible for the binding of signaling molecules. The cytoplasmic tail of PD-1 contains 2 tyrosine-based signaling motifs, an immunoreceptor tyrosine-based inhibition motif (ITIM) and an immunoreceptor tyrosine-based switch motif (ITSM). Following T-cell stimulation, PD 1 recruits the tyrosine phosphatases SHP-1 and SHP-2 to the ITSM motif within its cytoplasmic tail, leading to the dephosphorylation of effector molecules such as CD3 ζ , PKC θ and ZAP70 which are involved in the CD3 T-cell signaling cascade. The mechanism by which PD-1 down modulates T-cell responses is similar to, but distinct from that of CTLA-4 as both molecules regulate an overlapping set of signaling proteins. PD-1 was shown to be expressed on activated lymphocytes including peripheral CD4⁺ and CD8⁺ T-cells, B-cells, T regs and Natural Killer cells. Expression has also been shown

during thymic development on CD4-CD8- (double negative) T-cells as well as subsets of macrophages and dendritic cells. The ligands for PD-1 (PD-L1 and PD-L2) are constitutively expressed or can be induced in a variety of cell types, including non-hematopoietic tissues as well as in various tumors. Both ligands are type I transmembrane receptors containing both IgV- and IgC-like domains in the extracellular region and contain short cytoplasmic regions with no known signaling motifs. Binding of either PD-1 ligand to PD-1 inhibits T-cell activation triggered through the T-cell receptor. PD-L1 is expressed at low levels on various non-hematopoietic tissues, most notably on vascular endothelium, whereas PD-L2 protein is only detectably expressed on antigen-presenting cells found in lymphoid tissue or chronic inflammatory environments. PD-L2 is thought to control immune T-cell activation in lymphoid organs, whereas PD-L1 serves to dampen unwarranted T-cell function in peripheral tissues. Although healthy organs express little (if any) PD-L1, a variety of cancers were demonstrated to express abundant levels of this T-cell inhibitor. PD-1 has been suggested to regulate tumor-specific T-cell expansion in subjects with melanoma (MEL). This suggests that the PD-1/PD-L1 pathway plays a critical role in tumor immune evasion and should be considered as an attractive target for therapeutic intervention.

- 1.43 Pembrolizumab is a potent and highly selective humanized monoclonal antibody (mAb) of the IgG4/kappa isotype designed to directly block the interaction between PD-1 and its ligands, PD-L1 and PD-L2. Keytruda™ (pembrolizumab) has recently been approved in the United States for the treatment of patients with unresectable or metastatic melanoma and disease progression following ipilimumab and, if BRAF V600 mutation positive, a BRAF inhibitor.

1.5 Pharmaceutical and Therapeutic Background on Imiquimod

- 1.51 Imiquimod is a toll-like receptor seven (TLR7) agonist that activates the innate arm of the immune system. Imiquimod stimulates immune cells to secrete pro-inflammatory cytokines such as interferon- α (IFN- α), interleukin-6 (IL-6), and tumor necrosis factor- α (TNF- α). Cells activated by imiquimod include natural killer cells, macrophages and B-lymphocytes. Overall imiquimod acts on several levels, which appear to synergistically underlie the profound antitumoral activity of the compound. (1)

1.6 Preclinical and clinical Trial Data

- 1.61 The clinical trial data for pembrolizumab for the treatment of patients with metastatic melanoma has been previously published in detail. In summary, pembrolizumab induces durable remissions in a sizable minority of patients with metastatic melanoma (20-40%) with an acceptable safety profile of less than 10% grade 3 or 4 adverse events.
- 1.62 Imiquimod is a toll-like receptor 7 (TLR7) agonist approved for the treatment of basal cell carcinoma and genital warts. Imiquimod was tested in a randomized phase three study of patients with superficial basal cell carcinoma. (2) In this study, imiquimod induced histologic clearance in 80% of patients compared with 3% in the control arm with less than 10% of patients experiencing a severe (grade 3 or 4) adverse event. In the setting of genital warts, imiquimod 5% cleared 72-

84% of warts with a complete remission rate of 40-70% with few recurrences (5-19%). (3)

- 1.63 There are several reports demonstrating the clinical activity of imiquimod in treating cutaneous melanoma. In 2000, imiquimod 5% induced a complete remission in one patient with lentigo maligna melanoma. [1] In 2002, topical imiquimod 5% induced a complete remission in a patient with invasive melanoma however the patient did eventually develop lymph node metastases. [2] Also in 2002, Bong et al reported 3 patients with cutaneous metastases treated topical imiquimod with excellent responses in 2/3 of patients with the third patient achieving a response when combining imiquimod with intra-lesional interleukin-2. [3] Taken together, topical imiquimod is effective at controlling some patients with cutaneous melanoma but not at preventing distant metastases.
- 1.64 Topical imiquimod certainly has clinical activity in cutaneous melanoma metastases, however, often times additional immune modulation is necessary to achieve a complete response or prevent distant spread. With this in mind, Green et al performed a phase 1/2 study combining imiquimod with intralesional interleukin-2 in 13 patients demonstrating an overall response rate of 50% and complete response rate of 40%. [4] In a separate study, the combination of imiquimod 5% with BCG demonstrated complete remissions in 2 out of 3 patients. [5] In another case series of 11 patients with in-transit melanoma, 100% of patients responded to a combination of intra-lesional IL-2, imiquimod, and a topical retinoid. [6] Taken together, there is ample evidence that imiquimod is an effective at treating local cutaneous melanoma metastases however there are high rates of distant failure providing the rationale for combining imiquimod with systemic therapy.

1.7 Rationale

- 1.71 Approximately 20% of patients with metastatic melanoma are burdened with surgically unresectable cutaneous disease. The standard of care for these patients is systemic therapy as there are no FDA approved agents to apply directly to the skin. While systemic therapy can sometimes generate response in patients' cutaneous lesions, a topical therapy that could assist the systemic therapy would be highly desirable.
- 1.72 Multiple topical agents have been utilized to treat cutaneous melanoma with variable success. Imiquimod is a topical immune modulator thought to activate the toll-like receptor (TLR) pathway and help the body produce interferon locally to increase the activity of the immune system. Imiquimod is approved for the use of variety of skin disorders including basal cell carcinoma, actinic keratosis, and genital warts. Several studies have explored the efficacy of imiquimod to treat cutaneous melanoma and have demonstrated activity. There are no studies combining the use of imiquimod with pembrolizumab.
- 1.73 A case series reports successfully treated two patients with the combination of ipilimumab and imiquimod[7]. In both patients, cutaneous tumors substantially grew while on ipilimumab only to regress after the addition of imiquimod. Both patients tolerated the combination well and both patients have a durable remission of 9-12 months.

1.8 Rationale for Trial and Selected Subject Population

- 1.81 Despite recent improvement in the treatment of metastatic melanoma, the majority of patients still die from their disease providing a clear need to improve upon current treatments.
- 1.82 More specifically anti-PD1 agents such as pembrolizumab are capable of stimulating the patient's immune system by inhibiting the PD1/PDL1 axis. Given the ability of pembrolizumab to stimulate the patient's immune system, combining pembrolizumab with additional immune stimulation has the potential to provide additive or synergistic benefit when compared to single agent pembrolizumab.
- 1.83 Patients with metastatic melanoma and cutaneous metastases provide a unique opportunity to combining both topical and systemic therapy. We have previously demonstrated that the combination of imiquimod and ipilimumab is both safe and effective in two patients (under review).
- 1.84 The potential benefit of the combination of imiquimod and pembrolizumab remains to be tested in controlled studies.

1.9a Rationale for Fixed Dose of Pembrolizumab

- 1.9a1 The choice of the 200 mg Q3W as an appropriate dose for the switch to fixed dosing is based on simulations performed using the population PK model of pembrolizumab showing that the fixed dose of 200 mg every 3 weeks will provide exposures that 1) are optimally consistent with those obtained with the 2 mg/kg dose every 3 weeks, 2) will maintain individual patient exposures in the exposure range established in melanoma as associated with maximal efficacy response and 3) will maintain individual patients exposure in the exposure range established in melanoma that are well tolerated and safe.
- 1.9a2 A fixed dose regimen will simplify the dosing regimen to be more convenient for physicians and to reduce potential for dosing errors. A fixed dosing scheme will also reduce complexity in the logistical chain at treatment facilities and reduce wastage.

1.9b Rationale for dose of Imiquimod

The dose of imiquimod 5% applied Monday-Friday was selected on the basis of previous clinical studies demonstrating acceptable toxicity and efficacy profile in other skin conditions.

1.9c Rationale for Clinical Endpoints

- 1.9c1 As mentioned above, this is a pilot study to test both the safety and efficacy of the combination of pembrolizumab and imiquimod. Both safety and efficacy will be assessed individually.

- 1.9c11 Clinical Efficacy Endpoint- The expected single agent response rate of pembrolizumab is ~40% in the front line setting and ~25% when given after progression on ipilimumab. Given the small number of patients to be enrolled onto this trial, we will construct a 90% confidence interval for the proportion of patients who have a CR or PR on two consecutive evaluations at least 6 weeks among all the patients enrolled on this trial.
- 1.9c12 Clinical Safety Endpoint - Given the non-overlapping toxicities of pembrolizumab and imiquimod, we expect serious toxicities to occur at a rate similar to each drug individually. For example, pembrolizumab induces serious adverse events in ~10% of patient and imiquimod induces serious adverse events in 1-3% of patients. Therefore we expect ~10-13% of patient to experience a serious adverse event.

1.9d Biomarker Research

One of the largest unmet needs in improving the therapeutic potential of pembrolizumab is identifying reliable predictive biomarkers. In this study, the biomarker research will be exploratory in nature and will include assessing total tumor RNA through RNA seq and PDL1 expression through the use of immunohistochemistry. Attempts will then be made to associate molecular markers with clinical outcomes.

2.0 Goals

2.1 Primary

To gain preliminary data of the anti-tumor activity and safety profile of the combination of imiquimod and pembrolizumab in patients with unresectable cutaneous melanoma.

2.3 Correlative Research

To compare and contrast (in a hypothesis generating manner) the biomarker profiles of patients who have a confirmed CR or PR by RECIST criteria with patients who do not. Immunologic markers to be assessed include tumor-infiltrating lymphocytes (TIL), tumor expression of programmed death ligand one (PDL1), and toll-like receptor 7.

3.0 Patient Eligibility

3.1 Registration – Inclusion Criteria

- 3.11 Age \geq 18 years.
- 3.12 Histological confirmation of Stage IIIB, IIIC, IVM1a, IVM1b, or IVM1c that is not suitable for surgical resection.
- 3.13 Patients must not have received prior pembrolizumab or other anti-PD1/PDL1 therapies for their metastatic disease.

- 3.14 At least one cutaneous lesion that is amenable to treatment with topical imiquimod.
- 3.15 Measurable disease by RECIST as defined in Section 11.0.
- 3.16 ECOG Performance Status (PS) of 0 or 1 (Appendix I).
- 3.17 The following laboratory values obtained ≤ 14 days prior to registration.
- Absolute neutrophil count (ANC) $\geq 1500/\text{mm}^3$
 - Platelet count $\geq 100,000/\text{mm}^3$
 - Hemoglobin $> 9.0 \text{ g/dL}$ or $\geq 5.6 \text{ mmol/L}$ without transfusion or EPO dependency (within 7 days of assessment).
 - Serum total bilirubin $\leq 1.5 \times \text{ULN}$ or Direct bilirubin $\leq (\text{ULN})$ for subjects with total bilirubin levels $> 1.5 \text{ ULN}$
 - Aspartate transaminase (AST) $\leq 2.5 \times \text{ULN}$ or $\leq 5 \times \text{ULN}$ for subjects with liver metastases.
 - Albumin $\geq 2.5 \text{ mg/dL}$
 - Creatinine $\leq 1.5 \times$ upper limit of normal (ULN)
- NOTE:** Measured or calculated (per institutional standard) creatinine clearance is acceptable $\geq 60 \text{ mL/min}$ for subject with creatinine levels $> 1.5 \times$ institutional ULN. Calculated creatinine clearance can be used in place of creatinine or CrCl and must be $\geq 45 \text{ mL/min}$ using the Cockcroft-Gault formula below:

Cockcroft-Gault Equation:

$$\text{Creatinine clearance for males} = \frac{(140 - \text{age})(\text{weight in kg})}{(72)(\text{serum creatinine in mg/dL})}$$

$$\text{Creatinine clearance for females} = \frac{(140 - \text{age})(\text{weight in kg})(0.85)}{(72)(\text{serum creatinine in mg/dL})}$$

- 3.18 Negative urine or serum pregnancy test done ≤ 72 hours prior to first treatment, for women of childbearing potential only.

If the urine test is positive or cannot be confirmed as negative, a serum pregnancy test will be required.

- 3.19a Provide informed written consent.
- 3.19b Willing to return to enrolling institution for follow-up.
- 3.19c Willing to provide tissue from a newly obtained core or excisional biopsy of a tumor lesion in appropriate low risk cutaneous lesions.

NOTE: If the tissue biopsy is deemed to be of increased risk for the patient, the biopsy should not be performed and is optional.

NOTE: Newly-obtained is defined as a specimen obtained up to 42 days prior to registration where no anti-cancer therapy after the specimen was obtained and registration.

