3.2 Registration – Exclusion Criteria

3.21 Any of the following because this study involves an investigational agent whose genotoxic, mutagenic and teratogenic effects on the developing fetus and newborn are unknown:

- Pregnant women
- Nursing women
- Men or women of childbearing potential who are unwilling to employ adequate contraception

NOTE: Female subjects of childbearing potential should be willing to use 2 methods of birth control or be surgically sterile, or abstain from heterosexual activity for the course of the study through 120 days after the last dose of study medication (Reference Section 5.7.2). Subjects of childbearing potential are those who have not been surgically sterilized or have not been free from menses for > 1 year. Male subjects should agree to use an adequate method of contraception starting with the first dose of study therapy through 120 days after the last dose of study therapy. Abstain from heterosexual activity is also acceptable method of contraception for males.

- 3.22 Co-morbid systemic illnesses or other severe concurrent disease which, in the judgment of the investigator, would make the patient inappropriate for entry into this study or interfere significantly with the proper assessment of safety and toxicity of the prescribed regimens.
- 3.23 Known history of Human Immunodeficiency Virus (HIV) (HIV 1/2 antibodies).
- 3.24 Uncontrolled intercurrent illness including, but not limited to, ongoing or active infection, symptomatic congestive heart failure, unstable angina pectoris, cardiac arrhythmia, or psychiatric illness/social situations that would limit compliance with study requirements.
- 3.25 Receiving any other investigational agent which would be considered as a treatment for the primary neoplasm or used an investigational device ≤ 4 weeks from registration.
- 3.26 History of myocardial infarction ≤ 6 months, or congestive heart failure requiring use of ongoing maintenance therapy for life-threatening ventricular arrhythmias.
- 3.27 Known history of active TB (Bacillus Tuberculosis)
- 3.28 Hypersensitivity to pembrolizumab or any of its excipients.
- 3.29a Prior anti-cancer monoclonal antibody (mAb) ≤ 4 weeks prior to registration or who has not recovered (i.e., \leq Grade 1 or at baseline) from adverse events due to agents administered more than 4 weeks prior to registration

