- 3.29b Prior chemotherapy, targeted small molecule therapy, or radiation therapy ≤ 2 weeks prior to registration or who has not recovered (i.e., \leq Grade 1 or at baseline) from adverse events due to a previously administered agent.

Note: Subjects with \leq Grade 2 neuropathy are an exception to this criterion and may qualify for the study.

Note: If subject received major surgery, they must have recovered adequately from the toxicity and/or complications from the intervention prior to starting therapy.

- 3.29c Known secondary malignancy that has progressed within the last 3 years or requires active treatment. Exceptions include basal cell carcinoma of the skin or squamous cell carcinoma of the skin that has undergone potentially curative therapy or in situ cervical cancer.
- 3.29d Known central nervous system (CNS) metastases and/or carcinomatous meningitis.
- 3.29e Active autoimmune disease that has required systemic treatment in the past 2 years (i.e. with use of disease modifying agents, corticosteroids or immunosuppressive drugs). Replacement therapy (eg., thyroxine, insulin, or physiologic corticosteroid replacement therapy for adrenal or pituitary insufficiency, etc.) is not considered a form of systemic treatment.
- 3.29f History of (non-infectious) pneumonitis that required steroids or current pneumonitis.
- 3.29g Active infection requiring systemic therapy.
- 3.29h History or current evidence of any condition, therapy, or laboratory abnormality that might confound the results of the trial, interfere with the subject's participation for the full duration of the trial, or is not in the best interest of the subject to participate, in the opinion of the treating investigator.
- 3.29i Known psychiatric or substance abuse disorders that would interfere with cooperation with the requirements of the trial.
- 3.29j Received prior therapy with an anti-PD-1, anti-PD-L1, or anti-PD-L2 agent.
- 3.29k Known active Hepatitis B (e.g., HBsAg reactive) or Hepatitis C (e.g., HCV RNA [qualitative] is detected).
- 3.29l Received a live vaccine ≤ 30 days prior to registration.

Note: Seasonal influenza vaccines for injection are generally inactivated flu vaccines and are allowed; however intranasal influenza vaccines (e.g., Flu-Mist®) are live attenuated vaccines, and are not allowed.

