4.0 Test Schedule

Tests and Procedures	≤28 Days prior to Registration	Day 1 (+/-3 days) of each cycle	End of Treatment	Observation	
				Every 12 (+/- 2) weeks for months 24 thru 36 post registration	at progression
History and Physical Examination, wt, PS	X	X	X	X	X
Height	X				
Adverse Events Assessment	X	X	X	X	X
Pregnancy Test – Urine or Serum –HCG ¹		X ⁶			
CBC w/diff	X ²	X	X	X	X
Renal Profile: Sodium, Potassium, Chloride, Bicarbonate, Creatinine, Bun, Glucose	X ²	X	X	X	X
Albumin, bilirubin total and direct, alkaline phosphatase, total protein, AST, and ALT	X ²	X			
FT4 and TSH	X	X	X		
Disease Evaluation ³	X	X ⁴	X	X	X
Research Tissue Collection ^R		X ⁵			
Photograph of lesions	X	X	X	X	X

1. For women of childbearing potential only. Must be done ≤72 hours prior to registration.

2. ≤14 Days prior to Registration

3. Radiographic tumor imaging assessments must include CT scan, PET/CT, or MRI of the chest, abdomen, and pelvis. CT scan or MRI of the brain with contrast will only be performed if symptoms or signs of CNS metastasis are present. Use same imaging throughout the study.

4. At the completion of cycle 4 (approximately week 12) and then at completion of every 4th cycle (approximately every 12 weeks) thereafter (±7days) until PD.

5. Tissue specimens must be collected and submitted after registration but prior to the start of treatment, at completion of cycles 2 and 4 (approximately weeks 6 and 12).

6. For women of childbearing potential only. Must be done ≤ 72 hours prior to start of treatment. Must be repeated if pre-registration test is > 72 hours prior to the start of treatment.

R Research funded (see Section 19.0)

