8.0 Dosage Modification Based on Adverse Events

8.1 Dose-Modification Guidelines for Drug Related Adverse Events for Pembrolizumab

CTCAE System/Organ/Class (SOC)	ADVERSE EVENT	Hold Treatment for Grade	Timing for Restarting Treatment	Discontinue Subject
Gastrointestinal disorders	Diarrhea/Colitis	2-3	AE resolves to Grade 0-1	Toxicity does not resolve within 12 weeks of last dose or inability to reduce corticosteroid to 10mg or less of prednisone or equivalent per day within 12 weeks.
		4	Permanently discontinue	Permanently discontinue
Investigations	AST, ALT, or Blood bilirubin	2	AE resolves to Grade 0-1	AE does not resolve within 12 weeks of last dose
		3-4	Permanently discontinue (see exception below) ^a	Permanently discontinue
Metabolism and nutrition disorders	Glucose intolerance (Type 1 diabetes mellitus [if new onset] or Hyperglycemia)	Type 1 diabetes mellitus or 3-4	Hold pembrolizumab for new onset Type 1 diabetes mellitus or Grade 3-4 hyperglycemia associated with evidence of beta cell failure.	Resume pembrolizumab when patients are clinically and metabolically stable.
Endocrine disorders	Hypophysitis	2-3	AE resolves to Grade 0-1	AE does not resolve within 12 weeks of last dose or inability to reduce corticosteroid to 10mg or less of prednisone or equivalent per day within 12 weeks
		4	Permanently discontinue	Permanently discontinue
Endocrine disorders	Hyperthyroidism	3	AE resolves to Grade 0-1	AE does not resolve within 12 weeks of last dose or inability to reduce corticosteroid to 10 mg or less of prednisone or equivalent per day within 12 weeks.
		4	Permanently discontinue	Permanently discontinue

CTCAE System/Organ/Class (SOC)	ADVERSE EVENT	Hold Treatment for Grade	Timing for Restarting Treatment	Discontinue Subject
Endocrine disorders	Hypothyroidism	2-4	Therapy with pembrolizumab can be continued while treatment for the thyroid disorder is instituted	Therapy with pembrolizumab can be continued while treatment for the thyroid disorder is instituted.
General disorders and administration site conditions	Infusion reaction	3-4	Permanently discontinue	Permanently discontinue
Respiratory, thoracic and mediastinal disorders	Pneumonitis	2	AE resolves to Grade 0-1	AE does not resolve within 12 weeks of last dose or inability to reduce corticosteroid to 10mg or less of prednisone or equivalent per day within 12 weeks.
		3-4	Permanently discontinue	Permanently discontinue

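### Section 3.17 caps AST at entry but sets no limit for ALT, although ALT is measured at screening and the on-treatment liver rules treat the two enzymes alike

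*Combined protocol and SAP*

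**What the plan says.** The laboratory criteria in 3.17 cover neutrophils, platelets, hemoglobin, bilirubin, AST, albumin and creatinine. The only transaminase entry is "Aspartate transaminase (AST) $\leq 2.5 \times \text{ULN}$ or $\leq 5 \times \text{ULN}$ for subjects with liver metastases". ALT is not listed.

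The test schedule in 4.0 has one line for the liver panel, "Albumin, bilirubin total and direct, alkaline phosphatase, total protein, AST, and ALT". It is drawn within 14 days before registration and again on Day 1 of each cycle, so both enzymes are known when eligibility is decided.

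On treatment, the table in 8.1 is headed "Dose-Modification Guidelines for Drug Related Adverse Events for Pembrolizumab". One row covers AST, ALT and bilirubin together: hold at Grade 2, discontinue permanently at Grade 3 or 4. Footnote a adds a rule for patients with liver metastasis who start at Grade 2 in AST or ALT: they discontinue if the value rises by at least 50% over baseline for at least a week. Section 9.66 sets its management tiers on AST or ALT throughout.

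Other exclusions in 3.2 can reach a patient with raised ALT:
- 3.29a and 3.29b exclude patients who have not recovered "from adverse events due to agents administered more than 4 weeks prior to registration" or "from adverse events due to a previously administered agent".
- 3.29k excludes "Known active Hepatitis B (e.g., HBsAg reactive) or Hepatitis C".
- 3.22 excludes illness that, "in the judgment of the investigator, would make the patient inappropriate for entry into this study".
- 3.29h covers, among other things, a "laboratory abnormality that might confound the results of the trial".

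**The concern.** From screening onward, the protocol measures AST and ALT together and manages them together. The numeric entry rule is the exception, and the documents give no reason for it. As written, 3.17 does not stop a patient whose AST is acceptable but whose ALT is well above normal.

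Two things are at stake. The first is safety: a patient with unexplained liver injury could start pembrolizumab, for which 15.194 asks for close monitoring of liver tests because elevations may be early autoimmune hepatitis. The second is interpretation. The safety profile is part of the primary goal (2.1) and 10 patients are planned (16.1). The rules in 8.1 turn on whether an event is drug-related, and that call is harder when the baseline is already abnormal.

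**Working it through.** No arithmetic decides this point. It rests on setting the sections side by side.

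| Step | AST | ALT |
|---|---|---|
| Drawn within 14 days before registration (4.0) | yes | yes |
| Numeric entry limit, no liver metastases (3.17) | 2.5 × ULN | none |
| Numeric entry limit, liver metastases (3.17) | 5 × ULN | none |
| Drawn on Day 1 of each cycle (4.0) | yes | yes |
| Drug-related Grade 2: hold (8.1) | yes | yes |
| Drug-related Grade 3–4: discontinue (8.1) | yes | yes |
| Baseline-relative rule, liver metastasis with Grade 2 start (8.1 footnote a) | yes | yes |
| Management tiers (9.66) | yes | yes |

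The two columns differ only in the entry rows.

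**Who passes the numeric rule.** Section 9.662 pairs Grade 2 with values above 3 and below 5 × ULN, and 9.663 takes over at Grade 3. For AST, 3.17 keeps the starting value at or below 5 × ULN even with liver metastases. For ALT nothing does, so a patient with AST within limits and ALT at Grade 3 or above meets 3.17.

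**What the other exclusions remove.** Sections 3.29a and 3.29b deal with toxicity of earlier treatment. Section 3.29k requires hepatitis B or C to be both known and active. Sections 3.22 and 3.29h can apply to any patient but name no enzyme and give no number. What remains is a raised ALT with AST within limits, from some other or unexplained cause, that the investigator accepts.

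**What footnote a covers.** It needs both liver metastasis and a Grade 2 start. A patient without liver metastasis whose ALT is above 3 × ULN is outside it. So is a patient with liver metastasis whose ALT is at Grade 3. Neither has a stated baseline-relative rule.

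**Statistical figures.** The design figure in 16.1 is the one-sided 95% upper bound on the response rate with 0 responses in 10 patients: 1 − 0.05^(1/10) = 0.2589, which agrees with the stated 25.9%. It depends only on the number of patients and responses, so an ALT limit leaves it unchanged. The thresholds of the stopping rule in 16.61 are also unchanged.

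**The case against.** The strongest reply is that judgment already covers the case. The investigator has the ALT value before registration, 3.29h reaches laboratory abnormalities that could confound results, and 3.22 reaches illness that would interfere with assessing toxicity. Treatment starts at one site under a medical oncologist (6.9a). The bilirubin and albumin limits in 3.17 also screen out some patients with impaired liver function. All this stands and keeps the point small. It does not close the gap, since the protocol did not treat the same judgment as sufficient for AST.

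A second reply is that an on-treatment rule need not have a matching entry limit. Section 8.1 also acts on hyperglycemia and thyroid disorders, and 3.17 caps neither glucose nor thyroid tests although both are done before registration. That is fair: a missing match is not in itself an inconsistency. The case here is narrower. The protocol did choose to cap transaminases at entry, and capped one of two enzymes that it otherwise manages as a pair.

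A third reply is that footnote a shows raised baseline ALT was foreseen. It does, but only for liver metastasis with a Grade 2 start.

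A reader might infer more than the documents support:
- *That a patient entering with high ALT would at once have to be held or discontinued.* Section 8.1 covers drug-related events. Section 9.6 covers pembrolizumab toxicities and describes itself as guidance that does not displace clinical judgment. A pre-treatment value triggers neither.
- *That ALT events would go unrecorded because the table in 10.61 lists AST and not ALT.* Section 10.62 requires submission of related Grade 2 events and all Grade 3 and 4 events, and ALT is measured every cycle. No edit to 10.61 is needed for this point.

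**Conclusion.** The omission is certain on the text: 3.17 limits AST and not ALT, and no other entry criterion gives an ALT number. The consequence is conditional. It needs a patient with isolated ALT elevation who falls outside 3.29a, 3.29b and 3.29k and whom the investigator accepts under 3.22 and 3.29h. The documents give no frequency for such patients, so none is claimed.

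Where it happens, a patient with unexplained liver injury receives pembrolizumab and a later ALT rise is harder to attribute, though still assessable against the recorded baseline. This is a cheap improvement of low severity. It changes no efficacy result, sample size or stopping rule.

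**What to change.** Reword the transaminase line in 3.17 to: *AST and ALT ≤ 2.5 × ULN, or ≤ 5 × ULN for subjects with liver metastases*. The documents state no ALT threshold. Using the AST values is an assumption, based on the identical tiers that 8.1 and 9.66 apply to both enzymes, and the sponsor may prefer another number. Sections 8.1, footnote a and 9.66 can stay as they are.

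The cost is one line in an amendment. No extra test is needed, because ALT is already drawn in the same 14-day window. The downside is that an occasional patient with isolated ALT elevation would not be enrolled.
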